16.7. Appendix 7: Reporting Standards for Missing Data

16.7.1. Premature Withdrawals

Element	Reporting Detail
General	
 • Participants are considered to have completed the study if they remain on therapy (i.e., have not permanently discontinued IP) and satisfy one of the following: 
 - Randomly assigned to either treatment group, completed the randomized Maintenance Phase including Month 11/12 visits (with or without Month 11/12 study treatment) and did not enter the Extension Phase; - Randomly assigned to either treatment group, completed the randomized Maintenance Phase including Month 13, entered and completed the Extension Phase (defined as remaining on study until commercial supplies of the CAB LA + RPV LA Q8W regimen become locally available or development of CAB LA + RPV LA is terminated). 
Participants who withdraw from CAB LA + RPV LA and go into the Long-Term Follow Up Phase will be considered to have prematurely withdrawn from the study, even if they complete the 52-week follow-up Phase.
 
In addition to the 52-week Follow-Up phase required for participants who receive one or more injections with CAB LA or RPV LA, an in-clinic Follow-Up visit will be conducted approximately 4 weeks after the last dose of study medication for participants who withdraw during the oral lead-in phase and who were randomized to BIK with ongoing AEs, serious adverse events (SAEs) and any laboratory abnormalities that are considered to be AEs or potentially harmful to the participant, at the last on-study visit. Assessments at the Follow-up visit should reflect any ongoing complaints (e.g., blood draws to follow a laboratory abnormality). Follow-Up visits are not required for successful completion of the study.
 
 • Withdrawn subjects were not replaced in the study. • All available data from participants who were withdrawn from the study will be listed and all available planned data will be included in summary tables and figures, unless otherwise specified. • Withdrawal visits will be slotted as per Appendix 3: Assessment Windows or will be summarised as withdrawal visits.

16.7.2. Handling of Missing Data

Element	Reporting Detail
General	
 • Missing data occurs when any requested data is not provided, leading to blank fields on the collection instrument: • These data will be indicated by the use of a “blank” in participant listing displays. Unless all data for a specific visit are missing in which case the data is excluded from the table. • Answers such as “Not applicable” and “Not evaluable” are not considered to be missing data and should be displayed as such.

Element	Reporting Detail
Outliers	
 Any participants excluded from the summaries and/or statistical analyses will be documented along with the reason for exclusion in the clinical study report.

16.7.2.1. Handling of Missing and Partial Dates

Element	Reporting Detail
General	
 Partial dates will be displayed as captured in participant listing displays.
Adverse Events	
 The eCRF allows for the possibility of partial dates (i.e., only month and year) to be recorded for AE start and end dates; that is, the day of the month may be missing. In such a case, the following conventions will be applied for calculating the time to onset and the duration of the event: 
 Missing Start Day: First of the month will be used unless this is before the start date of study treatment; in this case the study treatment start date will be used and hence the event is considered On-treatment as per Appendix 4: Study Phases and Treatment State. Missing Stop Day: Last day of the month will be used, unless this is after the last contact date; in this case the last contact date will be used. Completely missing start or end dates will remain missing, with no imputation applied. Consequently, time to onset and duration of such events will be missing.
Concomitant Medications/Medical History	
 Partial dates for any concomitant medications recorded in the CRF will be imputed using the following convention: 
 If the partial date is a start date, a '01' will be used for the day and 'Jan' will be used for the month If the partial date is a stop date, a '28/29/30/31' will be used for the day (dependent on the month and year) and 'Dec' will be used for the month. For medications recorded in the eCRF as prior ART, the earlier of this imputed date or the day before Screening date will be used. For medications with completely missing start date, they will be considered started prior to the maintenance phase treatment start date. For medications with completely missing stop date, they will be considered ongoing unless recorded in eCRF as prior. For ART booster medications, the start and stop dates are not recorded in the database (i.e. missing), the dates will be imputed to be the same as the dates of their parent medications. The recorded partial or missing date will be displayed in listings.
Health outcomes	
 For the summary of individual item scores outputs, missing scores will not be computed.

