8.2.1. Analyses for Injection Site Reaction Adverse Events

Injection Site Reaction (ISR) adverse events of interest are those from study drug injections. For the summary of ISR adverse events by visit and maximum severity (overall and by common ISRs): ISRs will be assigned based on onset date to the most recent planned IM injection visit prior or equal to the AE onset date.

Maximum grade at each visit will be derived as the maximum grade among ISRs assigned to the particular visit, with consideration for whether the summary applies to a particular preferred term (vs. across preferred terms), associated to CAB and/or RPV, or stratification by subgroup (such as needle length, refer to Section 5.4.2).

ISRs (based on investigator discretion) from study drug injections will be attributed to the causal agent (CAB vs. RPV) when this can be determined specifically based on the side of injection administration and the side of the reported ISR (as collected in the eCRF). If the causal agent cannot be determined in cases where both drugs are given on one side or the ISR is reported non-specifically, then the attribution to a specific causal agent will remain unknown.

Common ISR adverse events during the Maintenance Phase are defined by MedDRA preferred terms including injection site pain, injection site induration, injection site nodules and preferred terms of any other ISR with $\geq 5\%$ participants in the Q2M arm. The same set of common terms will be applied to ‘overall’ (CAB and/or RPV), CAB alone, RPV alone.

ISRs will be attributed to the needle length specifically based on the side of injection administration and the side of the reported ISR (as collected in the eCRF). If the needle length cannot be determined due to both drugs given on the same side with different needle lengths, then the attribution to a needle length will remain unknown.

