16.4.1.1. Study Phases for AEs

Study Phase	Date range
Screen	Date < Maintenance Treatment Start Date
Maintenance	Q2M Arm (OLI and D2I): For participants continuing into Extension Phase: OLI: Maintenance Treatment Start Date ≤ Date < Date of Nominal Month 14 Injection Visit D2I: Maintenance Treatment Start Date ≤ Date < Date of Nominal Month 13 Injection Visit For participants not continuing into Extension Phase: Maintenance Treatment Start Date ≤ Date < LTFU ART Start Date (if applicable) Note: - For AEs leading to withdrawal and started on the same date as LTFU ART Start Date, Maintenance Phase, instead of Long-term Follow-up phase, will be assigned. - LTFU ART start date is not applicable for those who complete maintenance phase and transition to commercial supply.
	BIK Arm: For participants continuing into Extension Phase: Maintenance Treatment Start Date ≤ Date < min (Start Date of Extension Phase CAB/RPV oral lead-in, Date of first Extension Phase CAB/RPV injection) For participants not continuing into Extension Phase: Date ≥ Maintenance Treatment Start Date

Study Phase	Date range
Extension	
Participants continuing maintenance CAB LA + RPV LA into Extension Phase OLI: Date of Nominal Month 14 Injection Visit ≤ Date < LTFU ART Start Date (if applicable) D2I: Date of Nominal Month 13 Injection Visit ≤ Date < LTFU ART Start Date (if applicable)
 
Participants Switching from Maintenance BIK Arm to CAB LA + RPV LA: min (Start Date of Extension Phase CAB/RPV oral lead-in, Date of first Extension Phase CAB/RPV injection) ≤ Date < LTFU ART Start Date (if applicable)
 
Note: LTFU ART start date is not applicable for those who transition to commercial supply.

 • Date = AE Start date • Maintenance Treatment Start Date: refer to Treatment Start Date in Section 16.6.1 	

16.4.1.2. Study Phases for Lab assessments, ECG, Vital Signs, Health Outcomes, Protocol Deviations, and HIV associated/AIDS-defining conditions

Study Phase	Date range
Screen	Date ≤ Maintenance Treatment Start Date

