16.6. Appendix 6: Derived and Transformed Data

16.6.1. General

Multiple Measurements at One Analysis Time Point
 
 • If after window assignment there are multiple valid assessments of a parameter within the same window, then the following hierarchy will be used to determine the value to be used for summary statistics of observed values: 
 ○ the assessment closest to the window target Study Day (or target Injection Study Day if injection study day is used for assessment window slotting); ○ if there are multiple assessments equidistant from the target Study Day or target Injection Study Day, then for continuous variables the mean of these values will be used and for categorical variables the worse assessment. For HIV-1 RNA, the geometric mean of the number of copies will be used as opposed to the arithmetic mean • Assessments not chosen for use in summary statistics by this algorithm will still appear in the associated listings. Also, such valid assessments will be used when determining values of potential clinical concern for the 'any time' time point, and for any algorithm that has specific rules for which observation to use (e.g., Snapshot).

Treatment Start Date
 
Treatment start date is defined as follows:
 
 • Maintenance Phase 
 ○ For participants randomized to Q2M: Date of first dose of CAB + RPV (oral or injection) entered in the IP exposure CRF form. ○ For participants randomized to BIK: BIK regimen start date entered in the Maintenance Phase IP exposure CRF • Extension Phase 
 ○ For participants continuing CAB LA + RPV LA (Q2M): 
 - for Q2M OLI: Date of the nominal Month 14 injection date - for Q2M D2I: Date of the nominal Month 13 injection date ○ For participants switching from BIK to Q2M: Date of the nominal Month 13 Q2M injection date (BIK to D2I) or the oral CAB + RPV start date entered in the Extension Phase IP exposure CRF (BIK to OLI)

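### Adverse events with a missing start day: no floor at the first injection, so reactions to it can be dated before it in oral lead-in participants, and the floor at the switch from BIK is unclear

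*SAP*

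**What the plan says.** SAP 16.7.2.1 (Appendix 7) recognises the situation: "The eCRF allows for the possibility of partial dates (i.e., only month and year) to be recorded for AE start and end dates". For a missing start day the rule is "First of the month will be used unless this is before the start date of study treatment". The exception then reads "in this case the study treatment start date will be used and hence the event is considered On-treatment as per Appendix 4". No other floor is given.

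Five other parts of the SAP use the resulting date:

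- **Treatment start (16.6.1).** For the Q2M arm this is the "Date of first dose of CAB + RPV (oral or injection) entered in the IP exposure CRF form". An OLI participant's start is therefore the first oral dose, and 16.6.2 places that group's first injection at Month 1. The same table also defines a separate Extension Phase treatment start.
- **Phase for adverse events (16.4.1.1).** The date used is stated as "Date = AE Start date". For BIK participants who enter the Extension, Maintenance is "Maintenance Treatment Start Date ≤ Date < min (Start Date of Extension Phase CAB/RPV oral lead-in, Date of first Extension Phase CAB/RPV injection").
- **Oral lead-in period for adverse events (16.4.2.1).** It runs from treatment start up to, but not including, the first injection, and lies within the Maintenance Phase.
- **ISRs by visit (8.2.1).** They are "assigned based on onset date to the most recent planned IM injection visit prior or equal to the AE onset date".
- **Treatment state (16.4.3).** On-treatment criteria are not applied to adverse event summaries.

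**The concern.** The usual purpose of a floor in partial-date imputation is to stop an event being dated before the exposure that could have caused it. Here exposure changes more than once: at the first dose, at the first injection for those who start with oral tablets, and at the switch from BIK. The written floor clearly covers only the first of these.

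For OLI participants, and for BIK participants who switch through an oral lead-in, a reaction to the first injection can be dated before any injection was given. It then counts as an oral lead-in event, and the by-visit rule has no earlier injection visit to attach it to. No fallback is stated.

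For BIK participants who switch, an event that arose on CAB+RPV may be tabulated under BIK Maintenance. That would add an event to the comparator and remove one from the Switch Q2M displays.

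**Working it through.** The SAP gives no figure on this point, so there is nothing to reproduce. The check applies the rule literally:

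imputed start = later of (first of the recorded month, treatment start).

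**Assumptions.** Treatment start takes each of the 365 dates in 2021. The first OLI injection is 28, 30 or 31 days after treatment start (target Study Day 31 in 16.3.2.1). The switch is at Study Day 365, the Month 13 target in 16.3.2.3, so 364 days after start. Onset is spread evenly over days.

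**1. OLI, reaction on the day of the first injection.** Day 1 of the month, or the oral start date if that is later, precedes the injection unless the injection is on the 1st.
- Injection dates on the 1st: 12 of 365.
- Dated before the injection: 365 − 12 = 353, and 353/365 = 96.7%. The result is the same for all three lead-in lengths.
- Example: oral start 16 Mar 2021, injection and reaction 15 Apr 2021, recorded as Apr 2021. The imputed date is 1 Apr 2021, which lies in the oral lead-in period with no earlier injection visit.

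**2. OLI, onset 0 to 7 days after the first injection.** There are 365 × 8 = 2920 combinations. Cases escape if the injection is on the 1st or if onset falls in the next calendar month. In a month of n days:
- injection days 2 to n − 7 give 8 misdated onsets each, 8(n − 8) in all;
- the last seven injection days give 7 + 6 + … + 1 = 28;
- the total is 8n − 36.

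Over the year this is 8 × 365 − 12 × 36 = 2488, and 2488/2920 = 85.2%.

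**3. BIK switch, floor read as the Maintenance start.** Count the days from the switch to the end of its calendar month over all switch dates. A month of n days gives n(n + 1)/2.
- Total: 7 × 496 + 4 × 465 + 406 = 5738 participant-days.
- Correctly dated only when the switch is on the 1st: the 12 full months, 365 days.
- Dated back to BIK: 5738 − 365 = 5373, and 5373/5738 = 93.6%.
- Example: BIK start 16 Mar 2021, switch 15 Mar 2022, event 20 Mar 2022 recorded as Mar 2022. The imputed date is 1 Mar 2022, which is BIK Maintenance.

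**4. BIK switch, floor read as the Extension start.** None of the 5738 days is dated before the switch. For those who switch through an oral lead-in, the Extension start is again the first oral dose, so the problem in steps 1 and 2 recurs.

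**Who is protected.** Participants who go directly to injections in Maintenance are unaffected at their first injection, because that injection is their treatment start.

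**The case against.** **The floor may already be phase-specific.** SAP 16.4.1 classifies events relative to the treatment start in 16.6.1, which lists an Extension start as well as a Maintenance start. On that reading the switch is covered. This stands as a real ambiguity. Against it, 16.7.2.1 does not invoke the Extension start, and the Study Day definition in 16.6.1 uses the same treatment-start term for the Maintenance start. A reader might infer that the plan definitely credits post-switch events to BIK; the text does not settle that. The OLI problem survives either reading.

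**The rule is for time to onset and duration only.** It is introduced that way. But its own exception concludes on treatment state under Appendix 4, and the SAP gives no other imputation for adverse event dates.

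**The OLI consequence is minor.** This largely stands. The oral lead-in lies within Maintenance, so a back-dated reaction remains in the Q2M arm, in the overall Maintenance tables and in the ISR tables not split by visit. What suffers is the lead-in breakdown and the by-visit ISR displays (Tables 3.26 and 3.27 and the matching figures). A reader might infer a general bias in favour of CAB+RPV; at most that applies to switchers.

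**Events wholly before treatment are pulled in too.** Literally, an event whose whole month precedes treatment is moved to the start date. A reader might see a second defect here, but it is nearly empty: Appendix 2, footnote j, limits collection before Day 1 to certain related serious events.

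**Partial dates may be rare, and listings show them as captured.** Both points are fair. They limit the size of the problem but do not repair the rule.

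**Conclusion.** The point holds as a small defect in the safety derivations. The firm part is the missing floor at the first injection: on any reading, a stated rule can date a reaction before the injection that caused it and leave it without a visit. The share is 353 of 365 for onset on the injection day and about 85% for onset within 0 to 7 days.

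The switch part is conditional. If the floor is the Maintenance start, which is the more natural reading, about 94% of post-switch days in the switch month would be counted under BIK Maintenance, in favour of Switch Q2M.

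All these percentages apply only to events with a missing start day in one particular calendar month, and they assume even spread over the calendar. They are not shares of all adverse events or of all partial dates. The SAP does not say how many events qualify, and the number is probably small. The primary and key secondary efficacy analyses are untouched.

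**What to change.** Add two sentences to SAP 16.7.2.1:

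1. A study-drug ISR with a missing start day is never dated before the participant's first injection.
2. When the recorded month contains the first Extension CAB/RPV dose of a BIK participant, the imputed start is the later of day 1 and that dose date, unless the recorded end date precedes that dose.

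The cost is this wording and a few lines of derivation code. The first sentence has no real drawback.

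The second exchanges one error for another: events that began on BIK earlier in the switch month move to the new regimen. Under the same even-spread assumptions, pre-switch days in the switch month number n(n − 1)/2 per month, or 7 × 465 + 4 × 435 + 378 = 5373. That equals the number misdated now on the Maintenance-start reading, before the end-date exception rescues some. The case for the second sentence is therefore that it removes the ambiguity and errs in the usual conservative direction, not that it is more accurate overall.

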16.7.2.2. Handling of Missing data for Statistical Analysis

Element	Reporting Detail
Snapshot	
 • In the Snapshot dataset, participants without HIV-1 RNA data in the assessment window for the visit of interest (due to missing data or discontinuation of IP prior to the visit window) do not belong to 'HIV-1 RNA < 50 c/mL (or <200 c/mL)'. The nature of this missing data will be further classified in Snapshot summaries as either 'HIV-1 RNA≥50' or 'No Virologic Data at Week X'. See Appendix 9: Snapshot Algorithm Details.
Lipid Evaluable	
 • For subjects with lipid-modifying agent use, lipid assessments will be considered non-evaluable (equal to missing) after initiation without any imputation. • If participants take lipid modifying agents within 12 weeks prior to the start of the study treatment, all the post-baseline values will be non-evaluable. • The lipid evaluability rules will be used for the following displays: 
 Summary of Fasting TC/HDL ratio Change from Baseline Summary of Fasting Lipids Percentage Changes from Baseline Summary of Chemistry Changes from Baseline • All other displays of lipids (i.e. toxicity tables and NCEP tables) will use observed fasting data, without considering lipid evaluability. • The same rule of "lipid evaluable" will be applied to anthropometric parameters as specified in Section 8.5.3: 
 - Weight, Height and BMI - Waist circumferences - Hip circumference - CCI [REDACTED] - CCI [REDACTED] - Tanita scale parameters (total body fat percent, total body water percent, muscle mass, and bone mineral mass).

16.8. Appendix 8: Values of Potential Clinical Importance

Element	Reporting Detail
Laboratory Values and Adverse Events	
• The DAIDS grading for severity of laboratory toxicities and clinical adverse events is included in the protocol.• The central laboratory will flag lab parameter toxicities directly in the provided datasets.
ECG values	
• Defined as QTc > 500 msec or increase from baseline in QTc \geq 60 msec

16.9. Appendix 9: Snapshot Algorithm Details

Detailed Algorithm Steps

- Consider an analysis visit window for Month X as defined in Section [16.3.1](#)
- The HIV-1 RNA threshold of 50, 200 copies/mL will be analysed, respectively, in this study.
- The COVID-19 pandemic presents significant logistical challenges for many clinical sites around the world, with variable restrictions being placed on site resources and operations, and on an individual participant's ability to attend clinic visits. The snapshot algorithm is modified to allow for the presentation of full scope of COVID-19 relatedness. The analysis window 'Week 48' and HIV-1 RNA threshold of '50 c/mL' are used for the purpose of illustration. A participant's Snapshot response and reason at Week 48 are categorized as below.
 - HIV-1 RNA < 50 c/mL
 - HIV-1 RNA ≥ 50 c/mL
 - Data in window not below threshold
 - Non-COVID-19 related
 - Discontinued for lack of efficacy
 - Discontinued for other reason while not below threshold
 - Change in background therapy*
 - COVID-19 related
 - Discontinued for lack of efficacy
 - Discontinued for other reason while not below threshold
 - Change in background therapy*
 - No Virologic Data at Week 48 Window
 - Non-COVID-19 related
 - Discontinued study due to AE or death
 - Discontinued study for other reasons
 - Not evaluated or discontinued due to confirmed pregnancy**
 - On study but missing data in window
 - COVID-19 related
 - Discontinued study due to AE or death
 - Discontinued study for other reason
 - On study but missing data in window

- Note: since permanent changes in ART are not permitted in this protocol, all such participants who permanently change ART will be considered 'HIV-1 RNA \geq 50 c/mL' if the change is made prior to an analysis timepoint. Participants with protocol permitted oral bridging treatment, CAB+RPV or SOC (during COVID-19 pandemic due to the unavailability of the CAB/RPV IM injections and oral CAB+RPV), or a temporary change in ART by mistake prior to an analysis timepoint (e.g. participant took the ART different from study treatment during oral lead-in by mistake for a short period of time and then went back to the study treatment) will not be considered 'HIV-1 RNA \geq 50 c/mL' due to 'change in ART'.
- The steps in determining response and reasons are indicated in Table below, in the order stated.
- *Background therapy is not given to participants while on study. The "change in background therapy" in detailed steps below refers to the "change in ART" in this study.
- ** This category is not needed if no subject on the Q2M arm becomes pregnant and continues in the study.

Detailed steps

Please note that the following scenarios will NOT be penalized per Snapshot algorithm (i.e. please exclude these scenarios from **Conditions** 1-4).

- Dose reduction, dropping a component, or change in formulation (e.g. 'Tivicay + Kivexa' to 'Triumeq' with the identical ingredients)
- Protocol permitted temporary oral bridging, or temporary change in ART by mistake

Condition ('Week 48' indicates Week 48 window)	Response	Reasons
1. If non-permitted change in background therapy prior to Week 48		
○ not due to COVID-19	HIV-1 RNA \geq 50	Change in background therapy (non-COVID-19 related)
○ due to COVID-19	HIV-1 RNA \geq 50	Change in background therapy (COVID-19 related)
2. If permitted change^[a] in background therapy prior to Week 48 AND the latest on-treatment VL prior to/on the date of change is \geq 50 c/mL (NA to this study)		
○ not due to COVID-19	HIV-1 RNA \geq 50	Change in background therapy (non-COVID-19 related)

○ due to COVID-19	HIV-1 RNA \geq 50	Change in background therapy (COVID-19 related)
3. If non-permitted change in background therapy during Week 48		
○ Last on-treatment VL during Week 48 prior to/on the date of change \geq 50 c/mL	HIV-1 RNA \geq 50	Data in window not below 50
○ Last on-treatment VL during Week 48 prior to/on the date of change < 50 c/mL	HIV-1 RNA < 50	
○ No VL during Week 48 prior to/on the date of change and the change in background therapy is not due to COVID-19	HIV-1 RNA \geq 50	Change in background therapy (Non-COVID-19 related)
○ No VL during Week 48 prior to/on the date of change and the change in background therapy is due to COVID-19	HIV-1 RNA \geq 50	Change in background therapy (COVID-19 related)
4. If permitted change^[a] in background therapy during Week 48 AND the last on-treatment VL prior to/on the date of change is \geq 50 c/mL (NA to this study)		
4.1 This last on-treatment VL occurs prior to Week 48		
• The change in background therapy is not due to COVID-19	HIV-1 RNA \geq 50	Change in background therapy (non-COVID-19 related)
• The change in background therapy is due to COVID-19	HIV-1 RNA \geq 50	Change in background therapy (COVID-19 related)
4.2 This last on-treatment VL occurs during Week 48 but prior to/on the date of change	HIV-1 RNA \geq 50	Data in window not below 50
5. If none of the above conditions met		
5.1 On-treatment VL available during Week 48		
• Last on-treatment VL during Week 48 \geq 50 c/mL	HIV-1 RNA \geq 50	Data in window not below 50
• Last on-treatment VL during Week 48 < 50 c/mL	HIV-1 RNA < 50	
5.2 No on-treatment VL during Week 48		
5.2.1 If participants are still on study, i.e. a participant has not permanently discontinued the study treatment yet, or if a participant permanently discontinued		

the study treatment and the upper bound of analysis snapshot window is prior to the following date:
 
For Q2M arm: Min[max(Date of last CAB/RPV LA Dose + 67, Date of last oral dose+1), withdrawal date]
 
For BIK arm: Min (BIK Stop Date + 1, withdrawal date)
 
Note:
 
 • Last oral dose: may be CAB/RPV or SOC ART Oral Bridging where CAB/RPV is not available due to COVID-19 impact. • Withdrawal Date: date the participant failed to complete per corresponding conclusion form 		

5.2.1.1 If no on-treatment VL during Week 48 is not due to COVID-19
		

 • If no on-treatment VL is not due to confirmed pregnancy 	
No virologic data at Week 48 Window
	
On study but missing data in window (Non-COVID-19 related)

 • If no on-treatment VL is due to confirmed pregnancy (“while on-treatment”: data not evaluable) 	
No virologic data at Week 48 Window
	
Not evaluated or discontinued due to confirmed pregnancy(Non-COVID-19 related)

5.2.1.2 If no on-treatment VL during Week 48 is due to COVID-19
	
No virologic data at Week 48 Window
	
On study but missing data in window (COVID-19 related)

5.2.2 If participants withdraw before/during Week 48 due to
		

5.2.2.1 Non-COVID-19 related safety reasons (e.g. AE/death, liver chemistry stopping criteria, renal toxicity withdrawal criteria, QTc withdrawal criteria etc, as recorded in eCRF Conclusion form)
	
No virologic data at Week 48 Window
	
Disc due to AE/death (Non-COVID-19 related)

5.2.2.2 COVID-19 related safety reasons (e.g. AE/death, liver chemistry stopping criteria, renal toxicity withdrawal criteria, QTc withdrawal criteria etc, as recorded in eCRF Conclusion form)	No virologic data at Week 48 Window	Disc due to AE/death (COVID-19 related)
5.2.2.3 Non-safety and Non-COVID-19 related reasons (e.g. Lack of efficacy, protocol deviation, withdrew consent, loss to follow-up, study closed/terminated, investigator discretion etc, as recorded in eCRF Conclusion Form)		

 ◦ Last on-treatment VL <50 c/mL OR no on-treatment VL available during study 		

 • Withdrew not due to pregnancy 	No virologic Data at Week 48 Window	Disc for other reasons (Non-COVID-19 related)

 • Withdrew due to pregnancy 	No virologic Data at Week 48 Window	Not evaluated or discontinued due to confirmed pregnancy(Non-COVID-19 related)

 ◦ Last on-treatment VL ≥ 50 c/mL AND withdrawal due to Lack of efficacy 	HIV-1 RNA ≥ 50	Disc. for lack of efficacy (Non-COVID-19 related)

 ◦ Last on-treatment VL ≥ 50 c/mL AND withdrawal due to all other non-safety related reasons 	HIV-1 RNA ≥ 50	Disc. for other reason while not below 50 (Non-COVID-19 related)
5.2.2.4 Non-safety and COVID-19 related reasons (e.g. protocol deviation, withdrew consent, loss to follow-up, study closed/terminated, investigator discretion etc., as recorded in eCRF Conclusion Form)		

 • Last on-treatment VL <50 c/mL OR no on-treatment VL available during study 	No virologic Data at Week 48 Window	Disc for other reasons (COVID-19 related)

 • Last on-treatment VL ≥ 50 c/mL AND withdrawal due to Lack of efficacy 	HIV-1 RNA ≥ 50	Disc. for lack of efficacy (COVID-19 related)

 • Last on-treatment VL ≥ 50 c/mL AND withdrawal due to all other non-safety related reasons 	HIV-1 RNA ≥ 50	Disc. for other reason while not below 50 (COVID-19 related)

 • Excluding permitted change in background therapy where change or decision to change is made prior to/on the first on-treatment viral result 		

Examples from FDA guidanceData in Window

Virologic outcome should be determined by the last available measurement while the patient is on treatment and continued on trial within the time window:

- HIV-RNA = 580 copies/mL at Day 336, HIV-RNA below 50 copies/mL on Day 350. This should be categorized as HIV-RNA below 50 copies/mL.

No Data in Window

Discontinued study due to Adverse Event or Death:

- Any patient who discontinues because of an AE or death before the window should be classified as *Discontinued due to AE or Death* (as appropriate), regardless of the HIV-RNA result, even if the HIV-RNA is below 50 copies/mL at the time of discontinuation.
- However, if a patient has an HIV-RNA value in the time window and also discontinues in the time window, the viral load data should be used to classify the patient's response. This is the Virology First hierarchy:
 - HIV-RNA below 50 copies/mL at Day 336 and discontinues because of AE or even dies on Day 360 — this person is categorized as having HIV-RNA below 50 copies/mL.
 - HIV-RNA is 552 copies/mL on Day 336 and the patient discontinues on Day 360, the patient is categorized as having HIV-RNA greater than or equal to 50 copies/mL.

Discontinued for Other Reasons:

- Only patients who have achieved virologic suppression can be counted as *Discontinued for Other Reasons*.
- If a patient discontinues the study before the time window because of *lack of efficacy* then the patient should be included in the HIV-RNA greater than or equal to 50 row and not in the Discontinued for Other Reasons row.
- If a patient discontinues because of *subject withdrew consent* and his or her HIV-1 RNA result at the time of discontinuation was equal to or above 50 copies/mL, then he or she should be categorized as HIV-RNA greater than or equal to 50 and NOT as Discontinued for Other Reasons.
- If a patient discontinued because of *Lost to Follow-Up* and the last HIV-RNA result was 49 copies/mL, then the patient can be categorized as Discontinued for Other Reasons.
- If patients changed background treatment — *not permitted by protocol*— they should be considered an efficacy failure and captured in the HIV-RNA greater than or equal to 50 copies/mL row.

On study but missing data in window:

- If there are no data during Days 294 to 377, but there is an HIV-RNA below 50 copies/mL on Day 380, this patient should be considered *On Study but Missing Data in Window*.

- If there are no data during Days 294 to 377, but there is an HIV-RNA equal to or above 50 copies/mL on Day 280, this patient also should be classified as *On Study but Missing Data in Window*.

Not evaluated due to confirmed pregnancy:

Q2M subjects who became pregnant on study will be allowed to continue study treatment whereas BIK subjects will be withdrawn. HIV-1 RNA data will be treated as non-evaluable after confirmed pregnancy date as recorded on the eCRF, if a pregnant Q2M subject is allowed to continue.

